## 6.4 Device Labeling

This study will utilize shelf-stock devices. As such, no special labelling is required.

## 6.5 Treatment Allocation and Measures to Minimize Bias

In this single-arm study, the choice of the specific device type, size, number of lumens, and length required for an individual patient is left to the discretion of the clinician.

## 7 STUDY PROCEDURES AND ASSESSMENTS

- Study activities and their timing are summarized in the Schedule of Activities (SoA), Section 1.2.
- Protocol waivers or exemptions are not allowed.
- Adherence to the study design requirements, including those specified in the SoA, is essential and required for study conduct.
- All inclusion/exclusion criteria must be reviewed to confirm that potential participants meet all eligibility criteria.

### 7.1 Screening and Enrollment

After screening against inclusion/exclusion criteria, potential participants will be provided with detailed information about the study. If the potential participant, or parent/guardian in the case of those under 18 years of age, provides written informed consent, he/she will be enrolled in the study.

### 7.2 Medical History / Baseline Assessments

After enrollment, participant baseline and demographic information will be documented, including, but not limited to:

- Age
- Gender
- Primary diagnosis
- Limited medical history (e.g., vascular disease, coagulopathy, anticoagulant therapy)
- Reason for PICC insertion
- Expected duration of PICC use (i.e., short- vs. long-term)

### 7.3 Index Procedure

Choice of the specific PowerPICC type, size, number of lumens, and length required for an individual patient is left to the discretion of the clinician. The device and insertion site will be prepared according to the device specific IFU. The device will be inserted, and catheter tip location will be confirmed according to standard medical practice and according to the device specific IFU. Once proper placement is confirmed, the procedure will be completed, the catheter aspirated and flushed, and secured/stabilized according to the device specific IFU. The insertion site will be dressed according to the IFU and hospital-specific protocols.

#### 7.3.1 Procedure Data

After the PICC is in place, information about the insertion procedure will be documented, including, but not limited to:

- Date and time of insertion
- Catheter type, size, and length
- Insertion location
- Insertion procedure (e.g., components/accessories used including guidewires/stylets)
- Number of insertion attempts
- Stabilization method/securement method
- Dressing type
- Total procedure time
- Adverse events/complications (including but not limited to study endpoints such as laceration/perforation of vessel)
- Device deficiencies/failures
- Inserting clinician experience (e.g. years of experience, estimated number of PICCs inserted, education level)

### **7.3.2 Ease of Insertion Procedure Survey**

After the catheter is inserted and procedure data is recorded, the inserting clinician will complete a short survey to assess the performance of the guidewire/stylet.

## **7.4 Use and Maintenance Procedures**

The PowerPICC device will be used for therapy as medically required, according to the IFU and hospital protocol. The device will be maintained (i.e., flushing, fluid locking, cleansing) and the site maintained (i.e., cleansing, dressing) according to the device specific IFU, standard medical practice, and hospital protocols.

When the participant is treated in an acute-care setting, the catheter/site will be assessed daily until the device is removed or until they are discharged with the device in place (then treated as an outpatient). When the participant is treated in an outpatient setting, the catheter/site will be assessed at each therapy visit until the device is removed, or until 180 days post-insertion ( $\pm 14$  days), whichever comes first. For the purposes of endpoint calculations, PICCs remaining in place after 180 days will be considered to have completed therapy.

### **7.4.1 Use and Maintenance Data**

Device assessments will be conducted as part of the participant's routine medical care. Information from these assessments about the use and maintenance of the PICC will be documented, including, but not limited to:

- Catheter patency
- Performance of catheter/site maintenance procedures
- Type of use (i.e., IV therapy (e.g., antimicrobial, TPN, blood products), blood sampling, CVP monitoring, injection of contrast media)

- Adverse events/complications (including but not limited to study endpoints such as extravasation, VT, phlebitis, infection, etc.)
- Device deficiencies/failures (including but not limited to accidental dislodgement and occlusion)

## 7.5 Device Removal Procedure

The study device will be discontinued/removed when it is deemed medically appropriate by the participant's treating clinician (e.g., no longer needed, no longer functioning). Removal of the device will be performed according to the device specific IFU, standard medical practice, and hospital protocols.

### 7.5.1 Device Removal Data

At the time of device removal, the following data will be collected:

- Date and time of device removal
- Reason for removal (e.g., completion of therapy, device failure)
- Site condition

Note: Should the catheter remain in place through 180 days without removal, day 180, or the last study visit occurring  $180 \pm 14$  days, will be documented as the final catheter day for the purposes of dwell-time calculations.

## 8 PARTICIPANT DISCONTINUATION/WITHDRAWAL

### 8.1 Discontinuation/Withdrawal

- A participant may withdraw from the study at any time at his/her own request or may be withdrawn at any time at the discretion of the investigator or sponsor for safety, behavioral, compliance, or administrative reasons. This is expected to be uncommon.
- At the time of discontinuing from the study, no further data will be collected for the participant.
- If the participant withdraws consent for disclosure of future information, the sponsor may retain and continue to use any data collected before such a withdrawal of consent.
- Participants who withdraw or discontinue the study early (e.g., prior to PICC insertion) may be replaced.

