## 9 ADVERSE EVENTS AND DEVICE DEFICIENCIES

### 9.1 Definitions of Events

#### 9.1.1 Adverse Events (AEs)

An AE is defined as any untoward medical occurrence, unintended disease or injury, or untoward clinical signs (including abnormal laboratory findings) in subjects, users or other persons, whether or not related to the investigational medical device. In this study, AE collection will be limited to those occurring in the arm in which the device is inserted or upper torso, as well as any other undesirable clinical event judged to be related or likely related to the PowerPICC device or the suture or stabilization method used for securement of the device, regardless of anatomical region, that in the opinion of the investigator warrants reporting.

Pre-existing conditions should be considered as part of the participant's medical history and should not be reported as an AE unless there is a substantial increase in severity or frequency of the condition, which has not been attributed to natural history. Exacerbation of an existing condition should be reported as an AE if the event meets the protocol definition of an AE.

The clinical course of the event will be followed according to accepted standards of medical practice until the event resolves, stabilizes, or in the opinion of the Investigator, is no longer considered clinically significant. The Investigator must supply the Sponsor with information concerning the follow up and/or resolution of the AE.

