1.2 Discontinuation

- Table 1.2.1: Status at End of Study (*)

Safety Set

	Type of Device							
	PowerPICC (N=xxx)		PowerPICC SOLO (N=xxx)		PowerGroshong PICC (N=xxx)		Total (N=xxx)	
Completion status (CRF)	N	%	N	%	N	%	N	%
missing								
completed (removal and/or 180 days)								
withdrawal								
Overall (non-missing)								

	Type of Device							
	PowerPICC (N=xxx)		PowerPICC SOLO (N=xxx)		PowerGroshong PICC (N=xxx)		Total (N=xxx)	
Reason for withdrawal	N	%	N	%	N	%	N	%
missing								
withdrawal of consent								
lost to follow up								
death								
AE								
device deficiency								
other								
Overall (non-missing)								

Note 1: Reason for withdrawal only displayed for patients with study withdrawal.

	Type of Device							
	PowerPICC (N=xxx)		PowerPICC SOLO (N=xxx)		PowerGroshong PICC (N=xxx)		Total (N=xxx)	
Completion status	N	%	N	%	N	%	N	%
missing								
completed (removal and/or 180 days)								
death								
lost to follow up								
withdrawal								
Overall (non-missing)								

- Listing 1.2.1: Study Termination

Safety Set

Variables: Type of device, Participant, Date of study completion, Completion status, Reason for withdrawal, Specification of other reason, Date of death, EVS (yes/no), SAF (yes/no)

Note: Type of devices will be displayed as “by-variable” within a subtitle.

2 Demographic Data and Other Covariates

- Table 2.1: Participant Demographics – Frequencies

Safety Set

	Type of Device							
	PowerPICC (N=xxx)		PowerPICC SOLO (N=xxx)		PowerGroshong PICC (N=xxx)		Total (N=xxx)	
Gender	N	%	N	%	N	%	N	%
missing								
male								
female								
Overall (non-missing)								

	Type of Device							
	PowerPICC (N=xxx)		PowerPICC SOLO (N=xxx)		PowerGroshong PICC (N=xxx)		Total (N=xxx)	
Race	N	%	N	%	N	%	N	%
missing								
White								
Asian								
Black or African American								
other								
unknown								
Overall (non-missing)								

- Table 2.2: Participant Demographics – Basic Statistics

Safety Set

		Type of Device			Total (N=xxx)
		PowerPICC (N=xxx)	PowerPICC SOLO (N=xxx)	PowerGroshong PICC (N=xxx)	
Age [years] [^]	N				
	missing				
	mean				
	SD				
	minimum				
	1st quartile				
	median				
	3rd quartile				
	maximum				

Footnote 1: [^] Age at signing informed consent.

		Type of Device			Total (N=xxx)
		PowerPICC (N=xxx)	PowerPICC SOLO (N=xxx)	PowerGroshong PICC (N=xxx)	
Body height [cm]	N				
	missing				
	mean				
	SD				
	minimum				
	1st quartile				
	median				
	3rd quartile				

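### Protocol 8.1 lets a discretionary study withdrawal stop all data collection while the catheter is still in place, for reasons that can overlap the endpoints

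*Protocol*

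**What the plan says.** **Withdrawal rule (Protocol 8.1).** Apart from the participant's own request, a participant "may be withdrawn at any time at the discretion of the investigator or sponsor for safety, behavioral, compliance, or administrative reasons". The section adds "This is expected to be uncommon" and gives no rate. It then states: "At the time of discontinuing from the study, no further data will be collected for the participant". There is no exception for someone who still consents and still has the catheter. Data gathered before a withdrawal of consent are kept: "the sponsor may retain and continue to use any data collected before such a withdrawal of consent". Replacement is allowed: "Participants who withdraw or discontinue the study early (e.g., prior to PICC insertion) may be replaced". Exit before insertion is only an example there.

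**Recorded reasons (SAP Appendix A, Table 1.2.1, Safety Set).** The reasons for withdrawal include AE and "device deficiency". These rows concern leaving the study, not having the device taken out. Removal falls under the separate completed status, and a note says "Reason for withdrawal only displayed for patients with study withdrawal".

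**AE follow-up (Protocol 9.1.1).** A collected AE is followed until it resolves, stabilizes or is no longer clinically significant, and "The Investigator must supply the Sponsor with information concerning the follow up and/or resolution of the AE".

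**Analysis (SAP 4.4.1, 4.5.1, 4.5.2, 4.7).** Denominators are restricted to participants or devices with non-missing data. Nothing is imputed and no sensitivity analysis is stated. Missing endpoint data are reviewed at the data review meeting.

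**The concern.** Protocol 3 says there are no study-specific procedures, and Protocol 2.3.3 says the patient receives the device whether or not they take part. Withdrawing someone from the study for safety therefore spares them no study exposure. It only closes the record.

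The reasons for closing it can be related to the outcomes. Protocol 7.4.1 records VT, phlebitis, extravasation and infection as adverse events, and dislodgement and occlusion as device deficiencies. An AE or deficiency that prompts withdrawal may thus be an endpoint event, or an early sign of one.

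If the catheter is still in place at that point, the planned end of observation (removal or 180 ± 14 days, Protocol 4.3) has not been reached. Later complications, later loss of patency, and the removal date and reason would go uncollected. The removal reason decides therapy completion, the primary performance endpoint. Observation that ends for reasons linked to the outcome can bias the reported proportions, and complete-case denominators do not correct that.

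**Working it through.** **1. The plan's own figures.** Protocol 10.2 and SAP 1.2 assume 10% VT and n = 150 per device type. The half-width is 1.96 × √(0.10 × 0.90 / 150) = 0.048, so the stated ±4.8 points reproduces. No allowance for withdrawal is stated; the total is 3 × 150 = 450.

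**2. What is lost after a withdrawal with the catheter in place.**

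| Item | Status if 8.1 is applied |
|---|---|
| Endpoint event recorded before exit | Still counts |
| Outcome of the AE already reported | Required by 9.1.1, barred by 8.1: contradiction |
| Later VT or other complication | Not collected |
| Later patency | Not collected |
| Removal date and reason | Not collected |

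**3. How the SAP would treat these participants.** For VT, SAP 4.4.1 takes events from a tick on the AE page and divides by those with non-missing VT data. It does not say whether a participant who left early without a tick is missing or a no, so both are shown below. For completion, SAP 4.5.1 drops devices with missing success or failure. It also counts a catheter still in place as a success without repeating the day-180 condition. Read literally, a participant who left with the line in place could be scored a success. SAP 1.1 does restate the rule for lines in place after 180 days, so this reading may not be intended.

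**4. VT illustration (all counts assumed).** Take 15/150 = 10.0% as the truth.

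- Three VTs not captured: 12/147 = 8.2% if the three are missing, 12/150 = 8.0% if they are coded no.
- Eight participants withdrawn for some other event, of whom 25% to 50% (2 to 4) would later have had VT: 13/150 = 8.7% to 11/150 = 7.3% if coded no; 13/142 = 9.2% to 11/142 = 7.7% if missing.
- VT already ticked before withdrawal: no loss, 15/150 = 10.0%.
- Three participants without VT withdrawn and treated as missing: 15/147 = 10.2%, an upward shift.

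**5. Therapy-completion illustration (assumed).** Take 120/150 = 80.0% as the truth and let w true failures leave with the catheter in place.

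| w | Missing: 120/(150 − w) | Scored success: (120 + w)/150 |
|---|---|---|
| 3 | 120/147 = 81.6% (+1.6) | 123/150 = 82.0% (+2.0) |
| 8 | 120/142 = 84.5% (+4.5) | 128/150 = 85.3% (+5.3) |

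The assumed true rate matters little. In the missing case, w = 3 gives +1.4 points at a true 70% (105/147) and +1.8 at 90% (135/147). With w = 8 the shifts are +3.9 (105/142) and +5.1 (135/142).

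For scale, the same half-width formula at 80% and n = 150 gives 1.96 × √(0.80 × 0.20 / 150) = 6.4 points. Three such exits are small against that; eight are not negligible.

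**The case against.** The other side has substance.

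- **9.1.1 is a safeguard.** One might infer that a swollen arm closed as an AE before imaging necessarily loses its VT result. That follows only if 8.1 overrides 9.1.1. On the text of 9.1.1 the event is followed and its outcome supplied. This stands; what remains is the contradiction, and the loss of anything beyond that reported event.
- **A failing line is ordinarily removed.** Protocol 7.5 and 7.5.1 provide for removal of a catheter that no longer functions, with the reason recorded, and removal is study completion under 4.3. This stands for the usual course. It does not cover a participant withdrawn while the line is still in.
- **The two table reasons have a legitimate use.** The safety set requires placement, while the evaluable set requires successful placement (SAP 3.2, 3.3). Table 3.1 allows for unsuccessful placement on the safety set. Such a participant has no catheter to follow and does not enter the completion analysis. Deleting both rows would lose that information.
- **A table shell grants no authority to withdraw.** Protocol 8.1 names safety, not AE or device deficiency. True, but the shell shows that these reasons are expected among participants with a placement, and 8.1 does not limit what safety means.
- **The direction is not fixed.** Behavioral, compliance and administrative exits have no stated link to outcome, and 15/147 = 10.2% shows that VT can also move up. This stands.
- **Missing endpoints are reviewed and withdrawals are listed by reason.** This makes a pattern visible but does not recover the data.

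**Conclusion.** The point holds in a limited form. Protocol 8.1, read with SAP Table 1.2.1, permits observation to end while the catheter is in place because of events that overlap the endpoints, and the SAP has no analysis that addresses it. Protocol 8.1 and 9.1.1 contradict each other on whether data on an open AE continue after withdrawal.

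Therapy completion, patency and later complications are the exposed outcomes. VT is exposed only for events arising after exit, or for unconfirmed events if 8.1 prevails over 9.1.1.

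The size cannot be derived from the documents. The illustrations rest on assumed counts of 3 or 8 per 150, and the completion figures also assume that every lost participant is a true failure. With 3, the shifts are about 2 points or less. With 8, completion moves by roughly 4 to 5 points. Since withdrawal is expected to be uncommon, the smaller figure is the more plausible.

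A reader might infer that VT incidence is bound to be understated, or that failing devices systematically escape the count. The documents do not support either: events already recorded still count, AE follow-up is required, removal for device failure is a recorded outcome, and some exits would shift VT upward.

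**What to change.** 1. **Protocol 8.1.** State that after successful insertion an AE, a device deficiency, or a safety or compliance concern does not by itself end data collection while the catheter is in place. Routine-care data continue to removal or day 180 unless consent is withdrawn, the participant is lost to follow-up or dies, or the study or site is terminated (Protocol 13.6 reserves that right).
2. **Protocol 8.1 and 9.1.1.** Reconcile them by stating that AE follow-up under 9.1.1 continues.
3. **Completion CRF and SAP Table 1.2.1.** Restrict AE and device deficiency as withdrawal reasons to participants without an indwelling study catheter, such as those with failed placement. Otherwise record the event as an AE, a deficiency or a removal reason.
4. **SAP.** Add a sensitivity analysis that counts any AE or deficiency withdrawal with the catheter in place as a therapy-completion failure.

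The cost is protocol and SAP wording, a change to a CRF pick-list and one extra analysis. No visits are added, because the assessments are routine care. A few participants are followed longer, with some extra data entry at sites. The change concerns data collection only and leaves care decisions and the participant's right to withdraw untouched.

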### 8.2 Lost to Follow-Up

A participant will be considered lost to follow-up if he or she repeatedly fails to return for/complete therapy visits and is unable to be contacted by the study site.

## 9 ADVERSE EVENTS AND DEVICE DEFICIENCIES

### 9.1 Definitions of Events

#### 9.1.1 Adverse Events (AEs)

An AE is defined as any untoward medical occurrence, unintended disease or injury, or untoward clinical signs (including abnormal laboratory findings) in subjects, users or other persons, whether or not related to the investigational medical device. In this study, AE collection will be limited to those occurring in the arm in which the device is inserted or upper torso, as well as any other undesirable clinical event judged to be related or likely related to the PowerPICC device or the suture or stabilization method used for securement of the device, regardless of anatomical region, that in the opinion of the investigator warrants reporting.

Pre-existing conditions should be considered as part of the participant's medical history and should not be reported as an AE unless there is a substantial increase in severity or frequency of the condition, which has not been attributed to natural history. Exacerbation of an existing condition should be reported as an AE if the event meets the protocol definition of an AE.

The clinical course of the event will be followed according to accepted standards of medical practice until the event resolves, stabilizes, or in the opinion of the Investigator, is no longer considered clinically significant. The Investigator must supply the Sponsor with information concerning the follow up and/or resolution of the AE.

#### 9.1.2 Serious Adverse Events (SAEs)

A serious adverse event is defined by ISO 14155 as an adverse event that:

- a. led to death,
- b. led to serious deterioration in the health of the subject, that either resulted in
  - 1) a life-threatening illness or injury, or
  - 2) a permanent impairment of a body structure or a body function, or
  - 3) in-patient or prolonged hospitalization, or
  - 4) medical or surgical intervention to prevent life-threatening illness or injury or permanent impairment to a body structure or a body function,
- c. led to foetal distress, foetal death or a congenital abnormality or birth defect

NOTE: Planned hospitalization for a pre-existing condition, without serious deterioration in health, is not considered a serious adverse event. Likewise, conditions in the medical history leading to elective hospital stays (e.g. chemotherapy treatment) should not be considered as serious adverse events.

### **9.1.3 Adverse Device Effect (ADE) / Serious Adverse Device Effect (SADE)**

An adverse device effect is defined as any adverse event that is considered to be related to the use of an investigational medical device. This definition includes any event resulting from insufficiencies or inadequacies in the instructions for use, deployment, implantation, or operation or any malfunction of the investigational device (study device) and includes any event that is a result of a user error.

A serious adverse device effect (SADE) is defined as an ADE that has resulted in any of the consequences characteristic of an SAE.

### **9.1.4 Unanticipated (Serious) Adverse Device Effect (UADE/USADE)**

An unanticipated (serious) adverse device effect (UADE/USADE) is any (serious) adverse device effect on health or safety or any life-threatening problem or death caused by, or associated with, a study device, which by its nature, incidence, severity, or outcome has not been identified in the current instructions for use and/or current version of the risk analysis report, or any other unanticipated serious problem associated with a device that relates to the rights, safety or welfare of participants (see Section 2.3.1).

UADEs/USADEs will be reported to FDA as required by 21 CFR Part 812 and to the appropriate governing body per ISO 14155:2011(E).

## **9.2 Severity of Adverse Events**

Each AE shall be assessed for its severity, or the intensity of an event, experienced by the participant according to the criteria below.

Severity Rating	Description
Mild	Event, signs, or symptoms that do not interfere with the participant's daily activity, are usually considered self-limiting, can be treated with non-prescription type medications, and do not require medical intervention
Moderate	Event may interfere or cause low level inconvenience with the participant's daily activity. Requires medical intervention and/or treatment; however, unlikely to require hospitalization or be considered potentially life-threatening in nature
Severe	Event may cause significant discomfort to the participant and/or interferes with the participant's daily activity. Requires medical intervention and/or treatment to preclude a permanent impairment; may be life threatening and/or require hospitalization

